6.4 Screening, consent, and experimental procedures

Screening, consent for participants in Kinneret Sr Apartments

Staff from this site will introduce the researchers to older adults in Kinneret Sr Apartments for performing recruitment. Our team will meet with participants at a meeting room in Kinneret Sr Apartments. We will screen participants by asking their age and language (English or Spanish). We will also ask if they have a medical condition precluding balance test and/or physical activity (e.g., shortness of breath, unable to stand on the balance plate) or currently receiving treatment from a rehabilitation facility or have a metal implant. Finally, we will assess their cognition using the Memory Impairment Screen (MIS) test. It will take about 3-5 mins (total) per person.

We will complete the informed consent in a private and quiet place in Kinneret Sr. apartments for participants who meet the inclusion criteria. If the participant needs time to discuss taking part in this research study with family members, friends, and other care providers, we will reschedule a visit for completing surveys and tests.

If he/she indicates that she/he is ready and wants to participate in this research study, she/he will be asked to complete the questionnaires such as socio-demographics and fear of falling.

Procedure for contacting participants for timepoint 2:

Screening, consent for the general population (outside Kinneret)

Our team will meet with each participant (by appointment) in a private and quiet place at the UCF College of Nursing. Participants will complete a simple COVID-19 self-checker questionnaire before coming to the UCF campus. We will screen participants by asking their age and language (English or Spanish). We will also ask if they have a medical condition precluding balance test and/or physical activity (e.g., shortness of breath, unable to stand on the balance plate) or currently receiving treatment from a rehabilitation facility, or having a metal implant. Finally, we will assess their cognition using the Memory Impairment Screen (MIS) test. It will take about 3-5 mins (total) per person.

We will complete the informed consent in the participants who meet the inclusion criteria. If the participant needs time to discuss taking part in this research study with family members, friends, and other care providers, we will reschedule a visit for completing surveys and tests.

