If he/she indicates that she/he is ready and wants to participate in this research study, she/he will be asked to complete the questionnaires such as socio-demographics and fear of falling.

Procedure for contacting participants for timepoint 2:

Experimental procedures for both groups

We will assess the static balance performance using the BBS. Participants will take off their shoes and stand as still as possible on the balance plate with hands on their hips and eyes closed for 2-3 minutes. Participants will then complete the

dynamic balance performance test using the sit to stand by full standing up from a chair as many as possible within 30 seconds.

Participants will be stratified by the FRA matrix.¹⁷ We will continually evaluate across four groups (rational/ incongruent/ irrational/ congruent) to maintain equal cell distribution (30 OAs/group)*.

- 1) rational FRA: low FOF [Short Fall Efficacy Scale International (short FES-I) score ≤ 10] and aligned with normal balance (BBS score = 0-30).
- 2) incongruent FRA: low FOF (short FES-1 score ≤ 10) despite poor balance (BBS score= 31-100).
- 3) irrational FRA: high FOF (short FES-I score > 10) whereas normal balance (BBS score= 0-30).
- 4) congruent FRA: high FOF(short FES-I score > 10) and poor balance (BBS score= 31-100).¹⁷

**Please note: This is not an intervention study and subjects will not be assigned to the study group.*

They will perform the hand-grip strength and sit to stand tests. Hand-grip strength will be measured in kilograms (kg) as maximal isometric force achieved on a hand-grip dynamometer. This test will be administered with participants sitting in a chair with feet flat on the floor and the elbow bent at 90°. The dynamometer will be placed in the hand and adjusted so the palm side of the grip will be at the palm, and the front end will be lined up between the joints of the medial and distal phalanges. The grip size will be adjusted so that the second metacarpals were flat with a 90° bend at the knuckles. Participants will be asked to squeeze the strength gauge as hard as possible for 3–5 seconds. Three trials on each hand will be performed with 30-s of rest given between trials. Participants will complete the sit to stand by full standing up from a chair as many as possible within 30 seconds.⁷⁸

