Body composition will be tested, and all participants will be asked to empty their bladder, remove socks, shoes, and metal objects (e.g., watches, jewelry) before testing. The participants will be instructed to avoid exercise 6-12 hrs, eating 3-4 hrs, and drinking alcohol/coffee 24 hrs before the body composition test. We will obtain weight from a scale. Participants will be asked to stand for 10-15 mins before testing in a standing position or sit for 10-15 min for a seated position or lie down for 15 mins before testing in a supine position. The RA will present a photo of wipe hands and feet using an InBody tissue (optional).

The RA will also present photos of how to place the touch-type electrodes (labeled LT or RT) at the left and right ankles, middle fingers, and thumbs.

The participants will then place the touch-type electrodes to their left and right ankles, middle fingers, and thumbs. They will hold this position for one minute as the Bioelectrical Impedance Analysis (BIA) device; a minute electrical current will be conducted through the body to determine body composition. The participants will then remove the touch-type electrodes from their left and right ankles, middle fingers, and thumbs. The BIA machine is a widely used commercial device that is FDA approved. There are no risks or discomforts associated with the use of bioelectrical impedance analysis.

Participants will then be instructed to wear the ActiGraph GT9X Link wireless activity monitor on the non-dominant wrist for 7 consecutive days. Participants can remove the monitor only for imaging studies. Each participant will be asked to continue their normal activities while wearing the device. Written instructions will be provided to participants for the use of ActiGraph. The questionnaires and instructions will be provided in English or Spanish by bilingual research assistants (RAs) who will be trained and randomly monitored to ensure quality and consistency in administering questionnaires and tests. Participants will be

provided a phone number for the study team if they have questions about using the activity monitoring device.

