22.0 Consent Process

22.1

We will obtain IRB approval at the University of Central Florida. The PI or trained research assistants (RAs) will obtain consent from the subjects within the designed enrollment period.

Potential subjects will be contacted via phone to schedule the first visit for obtaining consent and completing surveys and tests.

For the residents in Kinneret Sr. apartments, the consent process will take place at a private or quiet room in Kinneret Sr. apartments. For the general population, the consent process will take place at a private room at the UCF, College of Nursing. If participants have a primary language is Spanish and cannot speak English, our research assistant, who fluent in both Spanish and English, will perform the consent using the Spanish language. The bilingual research assistant will explain the details in such a way that the participant understands what it would be like to take part in the research study and answer all questions.

The PI or RA will explain all aspects of the approved IRB consent form, including all required information (purpose, number of subjects, procedures, time requirements, potential risks, and benefits, measures to protect confidentiality) with subjects before obtaining consent. The subjects will be informed that participation in this study is voluntary. They are free to decline to be in the study or to withdraw from this study at any point without any negative consequence.

At the time potential subjects provide consent, they will be asked, for follow-up purposes, to provide their name, address, phone number, and email address along with the phone number and email addresses of their significant person or family member. Contact information will be kept separate from study records and will not be a permanent part of the study records.

Potential subjects will be told that they will participate in this study for approximately 9 days. They will participate in a screening, balance test, body composition test, and then wear activity-monitoring devices for 7 days.

Study subjects will be informed that study records will be kept as confidential as possible. No individual identifies will be used on any reports or publications resulting from this study. Study information will be coded and kept in locked files at all times. Only study personnel will have access to the files.

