The subject will read the informed consent form and will be able to hear a detailed description of the study and then will be given the informed consent document.

We will give subjects time to discuss taking part in this research study with family members, friends, and other care providers or take the written information home if they want, and we will reschedule a new visit for completing surveys and tests. If the subject indicates that he/she ready and wants to take part in this research study, we will perform the surveys and test as described above in the first visit. However, if the subject indicates that he/she does not want to take part in the research study, the consent process will stop.

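### The plan orders a maximal sit-to-stand test before body composition testing in the same visit, which conflicts with its own 6-12 h exercise restriction if that effort counts as exercise

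*Combined protocol and SAP*

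**What the plan says.** The preparation rule for BIA is in Section 6.4: "The participants will be instructed to avoid exercise 6-12 hrs, eating 3-4 hrs, and drinking alcohol/coffee 24 hrs before the body composition test".

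In the same section, under the experimental procedures for both groups, the written order is balance plate, sit-to-stand, grip strength, sit-to-stand again, body composition, then the activity monitor. Both strength tests ask for maximal effort. For the chair test: "Participants will complete the sit to stand by full standing up from a chair as many as possible within 30 seconds". For grip, participants are "asked to squeeze the strength gauge as hard as possible", and "Three trials on each hand will be performed with 30-s of rest given between trials". The only interval set immediately before BIA is time in the test posture: "Participants will be asked to stand for 10-15 mins before testing in a standing position or sit for 10-15 min for a seated position" (15 minutes if supine).

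On scheduling, Section 22.1 says: "Potential subjects will be contacted via phone to schedule the first visit for obtaining consent and completing surveys and tests". A person who is ready goes straight on: "we will perform the surveys and test as described above in the first visit". For a person who wants time to decide, Section 6.4 says "we will reschedule a visit for completing surveys and tests". Section 9.0 puts the total time for consent, questionnaires, tests, device instruction and the evaluation form at 105-158 minutes.

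**The concern.** The plan writes down a standardisation condition for BIA and then orders the visit so that the study's own tests appear to break it. Skeletal muscle mass and percent body fat are named in H2.1, H2.2 and H2.3, and percent body fat again in the Aim 3 hypothesis (Section 17.1). If the sponsor considers recent exercise relevant enough to restrict for 6-12 h, those variables should not be measured shortly after a test of maximal effort.

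A second, smaller gap is that the rule says participants will be instructed but not when. Nor does the text say that adherence is recorded. Without that record the analyst cannot separate prepared from unprepared measurements, and no sensitivity analysis is possible.

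**Working it through.** The plan gives no figure to reproduce here. The check compares the order of the tests with the length of the visit.

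**Step 1: order of the tests, by section**
- Section 6.2: static balance, sit-to-stand, BIA, grip, then the activity monitor.
- Section 6.4: balance plate, sit-to-stand, grip, sit-to-stand described again, BIA, then the activity monitor.
- Section 9.0: static and dynamic balance tests, body composition, then device instruction. Table 1 gives sit-to-stand as the dynamic balance test.

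Sit-to-stand comes before BIA in all three. Grip comes before BIA in Section 6.4 but after it in Section 6.2, so its position is unsettled.

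**Step 2: same visit or not**
- Section 6.4 moves directly from BIA to fitting the activity monitor, which is worn for the next 7 days. BIA therefore belongs to the testing visit and not to the end of the 9-day period.
- A rescheduled visit moves surveys and tests together, so it does not separate sit-to-stand from BIA.

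**Step 3: longest possible gap against each restriction**

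Total contact is 105-158 min = 105/60 to 158/60 = 1.75 to 2.63 h. No gap between two procedures in the visit can exceed 158 min.
- Exercise, shortest restriction 6 h = 360 min: 360 - 158 = 202 min short (3.37 h).
- Exercise, longest restriction 12 h = 720 min: 720 - 158 = 562 min short (9.37 h).
- Food, shortest restriction 3 h = 180 min: 180 - 158 = 22 min short (0.37 h), if the instruction is first given at that visit.
- Alcohol/coffee, 24 h = 1,440 min: 1,440 - 158 = 1,282 min short (21.37 h), under the same condition.

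**Step 4: which shortfalls are unavoidable**
- Exercise: the study itself causes the effort inside the visit, so advance instruction does not help. Only the order of the tests matters.
- Food and alcohol/coffee: these depend on when the participant is told. There are several contacts before testing: the scheduling call (22.1), the appointment for the general population (6.4), the rescheduled visit (6.4, 22.1) and the re-contact for timepoint 2 (13.1). Any of them could carry the instruction, but none is said to do so.

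**The case against.** The strongest counter-argument is that exercise is undefined. A 30-second chair test and grip squeezes of 3-5 seconds may not be what the author of the rule had in mind, and Section 15.1 rates the study's risks as no greater than those of daily life. This stands as a condition on the conclusion. However, the chair test asks for as many repetitions as the person can manage, and Section 15.1 names the sit-to-stand as a possible cause of fatigue. At the least, the plan should say whether these tests count.

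The order is also less fixed than Section 6.4 suggests. Section 6.2 puts grip after BIA, and Section 6.4 has no linking word between grip and BIA. This stands for grip, but not for sit-to-stand. No clock times are set, so the actual gap in minutes cannot be derived; only the upper bound can.

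Four stronger readings are tempting, and the documents do not support them:
- A reader might infer that the food and alcohol/coffee conditions cannot be met. They can, through the contacts listed in step 4. The gap is that the text does not link the instruction to those contacts.
- A reader might infer a bias between fall risk appraisal groups, because fitter people do more repetitions, or between timepoints, because people prepare better the second time. Both are conceivable, but no repetitions by group, effect of brief effort on impedance, or preparation data are given.
- A reader might infer that sit-to-stand is performed twice. Section 6.2 and Table 1 list it once, so the second description in Section 6.4 may be repeated text.
- A reader might suppose that unprepared participants could be measured at the second visit. Section 6.4 lets the device go back by mail or be left outside for pickup, so that visit may not be in person.

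Finally, Appendix H (BIA) and the study operation manual are not among the documents reviewed and may hold preparation details. The statements about what is not said apply to the protocol text only.

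**Conclusion.** The concern holds in a limited form. As ordered, a same-visit BIA after the sit-to-stand is at least 202 minutes short of the plan's own minimum exercise restriction. This rests on two assumptions: that the effort tests count as exercise, and that the 105-158 minute total is realistic. The conflict is firm for sit-to-stand and depends on which section is followed for grip. It affects the measurement conditions for skeletal muscle mass and percent body fat in Aim 2, and for percent body fat in Aim 3. The documents do not allow the size or direction of any error to be stated, and none is claimed.

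The timing of the food and alcohol/coffee instructions, and the recording of adherence, are missing detail and not a contradiction.

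**What to change.** Reconcile Sections 6.2, 6.4 and 9.0 on one order, with BIA before the sit-to-stand and grip tests at both timepoints. The static balance plate test can stay first, since with the fear-of-falling score it defines the fall risk appraisal group. Describe the sit-to-stand once. If anyone has already been measured in the old order, record which order was used, so that test order is not mixed up with timepoint in Aim 3.

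As a low-cost addition, state in Sections 6.4, 13.1 and 22.1 that the preparation instructions are given at the contact where the test visit is booked. Record hours since last meal, last alcohol or coffee, and last exercise. The Aim 2 models for skeletal muscle mass and percent body fat can then be repeated in participants who met the stated conditions, as a sensitivity analysis.

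Reordering adds no test time. The rest is a few sentences in the scheduling script and three fields on the form.

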1.0 Study Summary

Study Title	Technology-based fall risk assessments for older adults in low-income settings
Study Design	We will use a cross-sectional design to address our aims and test hypotheses.
Primary Objective	Examine the associations among fall risk appraisal, body composition, and physical activity.
Secondary Objective(s)	-Examine the feasibility of recruitment (e.g., how many older adults (OAs) need to be screened to recruit the sample?), especially during the COVID-19 pandemic, and acceptability of technologies and procedures for use among OAs in low-income settings. -Determine the dynamic relationships between fall risk appraisal, body composition, physical activity, and behavioral changes related to fear of falling
Research Intervention(s)/ Investigational Agent(s)	NA
IND/IDE #	NA
Study Population	Adults aged 60 years and older
Sample Size	120 participants for timepoint 1 60 participants for timepoint 2
Study Duration for individual participants	Total 9 days with two visits (105-158 mins, total)
Study Specific Abbreviations/ Definitions	Older Adults (OAs) Physical Activity (PA) Fall Risk appraisal (FRA) Fear of Falling (FOF) Assistive Health Technology (AHT) BTrackS Balance Plate (BBP) BTrackS Balance System (BBS) Body Mass Index (BMI) Bioelectrical Impedance Analysis (BIA) Fall-Efficacy Scale International (FES-I) Patient Health Questionnaire-9 (PHQ-9)

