Lastly, participants will be asked (using our evaluation form) about their reactions to the questions and technology (i.e., what they thought about the questionnaires and technology) and let them describe any concerns or problems in wearing the device (e.g., uncomfortable to wear during walking). We will provide feedback on the BBS and BIA test results, and participants will receive \$30 Walmart gift card upon completion of the study.

After 7 days of wearing ActiGraph, the participants will return the monitoring device via mail (we will provide pre-paid mailers) or schedule a date/time for picking it up. Participants will leave the device in front of their place.

- Please see Appendix A for a demographic survey
- Please see Appendix B for the Memory Impairment Screen (MIS)
- Please see Appendix C for Patient Health Questionnaire-9 (PHQ-9)
- Please see Appendix D for the Geriatric Anxiety Inventory-Short form (GAI-SF) and Day-to-Day Experiences with the trait Mindful Attention Awareness Scale (MAAS).
- Please see Appendix E for Short Fall Efficacy Scale International (short FES-I) and behavioral changes related to fear of falling
- Please see Appendix F for hand-grip strength test and static balance performance test
- Please see Appendix G for dynamic balance performance test (Sit to stand) and
- Please see Appendix H for Bioelectrical Impedance Analysis (BIA)
- Please see Appendix I for ActiGraph GT9X Link wireless activity monitors and the Rapid Assessment of Physical Activity (RAPA)
- Please see Appendix J for Evaluation form of acceptability of technology and procedures and the short version of Senior Technology Acceptance

6.5 *NA*, No plan for long-term follow-up in this study.

6.6 *NA*

7.0 **Data and Specimen Banking***

NA

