9.0 Study Timelines*

Participants will need about 105-158 minutes (total) to obtain consent and complete the questionnaires (e.g., socio-demographic, FOF, PHQ-9, fall risk, frailty, social network), the static and dynamic balance performance tests, body composition testing, learn how to wear the ActiGraph GT9X Link wireless activity monitor, and to complete the evaluation form of acceptability of technology and procedures.

Table 2. Timeline of activities and tasks to be accomplished during the proposed 2-year grant period

Activity	Year Month	1												2											
		1	2	3	4	5	6	7	8	9	10	11	12	1	2	3	4	5	6	7	8	9	10	11	12
Convene team, develop a study operation manual, staffing training, and set up database		█	█	█																					
Screen, recruit, enrollment, inform consent, data collection, follow-up, and data management					█	█	█	█	█	█	█	█	█	█	█	█	█	█	█	█	█	█	█	█	█
Interim analyses										█	█	█	█	█	█	█	█	█	█	█	█	█	█	█	
Final analyses																									
Dissemination and final grant report																									

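### Section 6.4 places the question on problems wearing the monitor before the 7-day wear, and the second visit that could hold it has no described content

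*Combined protocol and SAP*

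**What the plan says.** Section 6.4, under the experimental procedures for both groups, follows the order of the session. After the balance, grip, sit-to-stand and body composition tests: "Participants will then be instructed to wear the ActiGraph GT9X Link wireless activity monitor on the non-dominant wrist for 7 consecutive days". The form comes next: "Lastly, participants will be asked (using our evaluation form) about their reactions to the questions and technology". Participants are also to "describe any concerns or problems in wearing the device (e.g., uncomfortable to wear during walking". That paragraph ends with feedback on two of the tests and the gift card, which is given when the study is completed.

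The following paragraph covers the end of wear: "After 7 days of wearing ActiGraph, the participants will return the monitoring device via mail (we will provide pre-paid mailers", or a pick-up is scheduled. For the pick-up, "Participants will leave the device in front of their place".

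On visits, section 1.0 gives "Total 9 days with two visits (105-158 mins, total". Section 13.5 pays the gift card after the second visit. Section 22.0 describes the first: "Potential subjects will be contacted via phone to schedule the first visit for obtaining consent and completing surveys and tests". No section describes what is done at the second.

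Section 17.1 bases the acceptability part of Aim 1 on the evaluation form and participants' recommendations. Responses are coded, grouped into categories and counted.

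**The concern.** A question about discomfort while walking with the device can be answered from experience only by someone who has worn it. In the written order the participant has just been shown how to put it on. An answer given then says what the person expects, and the problems that emerge over a week at home (irritation, sleep, bathing, forgetting) have not yet had the chance to occur.

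Acceptability of the technologies is one of the two parts of Aim 1, which section 1.0 lists as a secondary objective. The monitor is the only device used at home over several days, so it is where early questioning loses most. The likely direction of error is too few reported problems, which would make the device look more acceptable than it is when a larger study is planned from these results.

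**Working it through.** No sample size, power or error rate bears on this point. The check sets the procedure order, visit count and analysis text side by side.

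1. **Order in section 6.4.** Fitting and instruction, then the form (introduced as the last step), then the paragraph on what follows 7 days of wear. Read in sequence, the form precedes the wear.

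2. **What is described after wear.** Mail return or doorstep pick-up. Neither route includes a form, a call or an interview.

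3. **Section 22.0.** The surveys and tests are put at the first visit. The account given to participants lists screening, balance test, body composition test and then 7 days of wear, with nothing after it.

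4. **Section 17.1, Aim 1.** At most 3% missing values per item are expected, on the ground that data are collected in person on site. For 120 participants that is 0.03 × 120 = 3.6, or about 4 missing answers. A no-contact return offers no on-site occasion after wear, so this expectation fits either a form at visit 1 or an in-person visit 2. It does not settle which.

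5. **Calendar.** One day for visit 1, 7 days of wear and one day for visit 2 give 1 + 7 + 1 = 9 days, the duration in section 1.0. This is my inference, but it fits a post-wear visit at which the form could be completed. The documents neither confirm nor exclude it.

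6. **Who would be affected.** At timepoint 1, up to 120 participants would answer the wearable items before any wear in the study. The roughly 60 at timepoint 2 are drawn from those 120 (section 13.1), so they come with one earlier wear period. The items on the questionnaires, balance plate and body composition device concern things already done by the time of the form, so early completion does not harm them.

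Steps 1 to 3 point to early completion, step 5 allows late completion, and step 4 is neutral. The early reading is the written sequence; the late reading has to be inferred.

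**The case against.** The strongest reply is that nothing assigns the form to a day or a visit. Two visits are stated, the calendar fits a visit after wear, and the gift card stands in the same paragraph as the form although section 13.5 places it after visit 2. At least one item in that paragraph therefore follows the 7 days, so paragraph order alone does not fix the timing. The wording about walking may itself show that post-wear completion was intended. The form is in Appendix J, which is not in the text I had and may state when it is used. All of this stands, and it rules out saying that the form is definitely completed at the fitting.

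A reader might go further in two ways that the documents do not support:

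- **That section 9.0 proves one session.** It lists time to "learn how to wear the ActiGraph GT9X Link wireless activity monitor, and to complete the evaluation form of acceptability of technology and procedures" within 105-158 minutes. Section 1.0 gives those minutes as the total alongside two visits, so the list does not place the two activities at one visit.
- **That Aim 1 cannot measure acceptability of the monitor.** Section 17.1 also reports the proportion who completed all procedures, which reflects the wear period. The form covers other technologies, and timepoint 2 participants have worn the monitor before. These are partial substitutes: completion does not reveal discomfort or its reasons, and timepoint 2 reaches only about half the sample, limited to those who agreed to future contact.

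The objection does not remove the need for a change. Visit 2 has no described content, a mailed or doorstep return is hard to reconcile with a visit at all, and assistants who follow section 6.4 as written would ask the wearing question too early.

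**Conclusion.** The point holds as a conditional one. If the written order of section 6.4 is followed, up to 120 timepoint 1 answers on the wearable describe expectation, and the Aim 1 count of wearing problems may be too low. The amount of under-reporting cannot be calculated, because the documents give no expected frequency of such problems.

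This rests on two assumptions: that staff follow the paragraph order, and that Appendix J does not state a later time. If the team already intends completion at a post-wear visit 2, the data are sound and only the text needs correcting, so that all assistants do the same thing. The rest of the form, the completion proportion and the Aim 2 analyses are untouched. I class this as a cheap improvement: more than a missing detail, because the sequence as written gives a worse measure, but not a flaw that defeats Aim 1.

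**What to change.** - In sections 6.4 and 9.0, state that the evaluation-form items on the monitor are completed after day 7: at visit 2, by a short phone call, or on a sheet placed in the pre-paid mailer that is already provided.
- Keep the items on the questionnaires, balance plate and body composition device at visit 1, while the experience is fresh.
- Describe what happens at visit 2 and reconcile it with the mail or doorstep return, so that sections 1.0, 6.4, 13.5 and 22.0 agree.

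The cost is a few sentences and either a call or a one-page sheet per participant. The downside is that some sheets may not be returned. If the mail route is used, the 3% missing-value expectation in section 17.1 no longer follows for these items, because its stated ground is in-person collection. Report the number of participants who answered them alongside the frequencies.
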